For time-to-event secondary endpoints, such as CMV reactivation at pre-specified thresholds, the Kaplan-Meier method will be used to estimate the probability of not experiencing the event by Day 28 for each treatment group. A 95% confidence interval for the between-group difference in event rates will be constructed using the Greenwood variance estimator. Between-group comparisons will be performed using a Z-test based on the Kaplan-Meier survival function estimates. Where applicable, Bonferroni correction will be used to adjust for multiple comparisons across secondary endpoints.

[figure not shown]
Additionally, multivariable models will be constructed for the primary endpoint (RSFDs) and other secondary outcomes to adjust for baseline characteristics and known risk factors for CMV reactivation. These models may include generalized linear models (GLMs) or the semiparametric method of Davidian et al., depending on the outcome type and distributional assumptions. The covariates considered will correspond to those outlined under exploratory objectives in Protocol Section 5.3.

As a secondary objective, we will assess whether the treatment effect varies by treatment period (i.e., during vs. post-drug exposure). Specifically, for mortality, we will test for treatment-by-period interaction to explore whether the timing of Ganciclovir exposure modifies the risk of death. If interaction is present, stratified or time-varying effect models will be considered in post hoc exploratory analyses.

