9. SAFETY ANALYSES

A summary table of MedDRA-coded adverse events (AEs) will be generated, displaying the frequency and percentage of participants experiencing each AE by treatment group, system organ class (SOC), and preferred term. In addition, a comprehensive listing of all reported AEs will be provided. This listing will include onset date, verbatim term, MedDRA code, SAE/EAE classification, study day, severity grade, relationship to study drug, outcome, and duration (in days).

Deaths will be summarized separately by treatment group, as described in Section 2.2. A Kaplan–Meier survival analysis will be conducted to estimate the time-to-death distribution for each arm. Survival curves will be compared using the log-rank test. A Cox proportional hazards model will also be used to estimate the hazard ratio (HR) and 95% confidence interval (CI) for mortality between groups, adjusting for baseline creatinine clearance. In addition, subgroup analyses will be conducted stratified by baseline creatinine clearance (≥ 60 vs. < 60 mL/min).

Survival analyses will be performed across multiple time windows: through Day 28 and Day 180 (± 42 days). Participants lost to follow-up will be censored at their last known survival date.

To further explore potential differences in mortality risk across treatment phases, an interaction analysis will be conducted between treatment assignment and treatment period (during-treatment vs. post-treatment). This analysis will help assess whether the effect of treatment on mortality differs between the period of active drug administration and the post-treatment period.

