11. ADDITIONAL ANALYSES

Additional analyses will be specifically described in the companion document, GRAIL 3 Statistical Analysis Plan for Exploratory and Post Hoc Analyses. These analyses are outside the scope of the FSR.

1. Subgroup analyses will be conducted to explore potential treatment effects on RSFDs and mortality across the following baseline factors:
 - Study site
 - Covid-19
 - Ventilation type
 - Sex, age, race
 - Severity scores
 - Underlying conditions
 - CMV reactivation at randomization
2. To assess potential hematopoietic toxicities and their clinical relevance, we will conduct the following analyses:
 - Comparison of lymphocyte and monocyte counts between treatment arms.
 - Stratified analyses of RSFDs and mortality by baseline lymphopenia and monocytopenia severity at predefined thresholds: <1000 cells/ μ L, <500 cells/ μ L, <100 cells/ μ L
3. Ganciclovir (GCV) may cause hepatic, pancreatic, or renal toxicity in critically ill patients. Potential toxicities will be evaluated by comparing key laboratory markers between treatment arms:
 - Hepatic: alanine transaminase (ALT)
 - Pancreatic: lipase, amylase
 - Renal: cystatin C
4. Potential neurologic toxicities of Ganciclovir will be explored, including possible associations with delirium, seizure, or cerebrovascular events. The following measures will be compared between treatment arms:
 - Delirium scores
 - Incidence of seizures
 - Incidence of stroke
5. Ganciclovir exposure may increase the risk of arrhythmias in critically ill patients. Arrhythmic events will be summarized by treatment arm, and comparisons will be made to evaluate potential cardiotoxic effects of the study drug.
6. To explore potential toxicities or complications associated with Ganciclovir, clinical conditions present at or immediately prior to death will be summarized by treatment arm. Causes of death will be tabulated and compared using appropriate statistical methods (e.g., chi-square or Fisher's exact test).
7. To evaluate the immunologic effects of Ganciclovir and CMV suppression, we will assess cytokine and proteomic responses by treatment arm. For individual cytokines, peak levels and area under the curve (AUC) over the first 7 days will be compared between randomization groups, with adjustment for baseline values.
8. Ganciclovir Exposure and Pharmacokinetics (PK) analysis: Unusually high drug levels in critically ill patients may increase toxicity.

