6.2.2 Secondary endpoints

[figure not shown]
For the quantitative secondary endpoints (including a key secondary endpoint of VFDs or ventilator-free days), the same method as described in the analysis plan for the primary endpoint will be used. For time to event endpoints including CMV reactivation at given thresholds, the Kaplan-Meier method will be used to estimate the probability of not experiencing CMV reactivation by Day 28 for each group. A 95% confidence interval about the group difference in event rates will be computed using the two Kaplan-Meier estimates and the two Greenwood variance estimates. Based on these estimates, a Z-statistic will be used for testing for difference in the group event rates. The multiple testing problem will be handled using a Bonferroni correction, whenever such situations arise. Additionally, multivariate models will be built for the primary endpoint (RSFD) as well as other secondary endpoints, after adjusting for baseline subject characteristics and risk factors for CMV reactivation, using generalized linear models or the semiparametric efficient and robust method of Davidian et al. [89, 90]. The list of baseline characteristics to be considered for adjustment are those listed in (1) under the Exploratory Objectives/Endpoints (Section 5.3). We will repeat the above analyses in several subgroups (separately) as well, including those who are PCR negative at baseline, as well as those that have septic shock, pneumonia, unilateral infiltrates, or lymphopenia at the time of randomization, and by age and sex. In addition, we will repeat the above analyses in the following subgroups as follows: (1) VFDs in those on invasive mechanical ventilation at randomization; (2) RSFDs in those on invasive mechanical ventilation at randomization; (3) RSFDs in those on NIV/high flow at randomization; (4) Intubation after enrollment in those on NIV/HFNC at randomization (i.e. does ganciclovir affect the need for intubation in this subgroup?); (5) RSFDs according to COVID-19 status at randomization; and (6) CMV detection in plasma by day 28 (28 (>0 IU/mL, >1000 IU/mL) in those with invasive mechanical ventilation vs. NIV/high flow at randomization.

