6.2.4 Other pre-specified analyses

Primary analysis, cITT, mITT, and survivors

Ideally, any patient randomized would be included in the conventionally defined ITT analysis cohort. Nonetheless in an emergency care setting, such as this study, the following unusual but important scenario will need to be considered: a patient is eligible and randomized but by the time of drug delivery no longer meets eligibility criteria and thus, should have been excluded.

Accordingly, it is intended that patients randomized but not having drug/placebo delivered will not be included in the primary analysis cohort. The integrity of randomization shall remain preserved, as the decision to deliver drug/placebo is determined a priori and completely independent of treatment assignment (14). If a participant is withdrawn from the study before a dose of study drug is given, no study procedures will be performed and no study data will be collected, and these participants will be excluded from the primary analysis. However, if a participant is withdrawn after receipt of study drug, safety procedures (e.g. monitoring of

creatinine and CBC with differential) will continue for another 48 hours, no study biosamples will be obtained, and study data in the medical record will continue to be collected per protocol (e.g. respiratory-support-free days), and they will be included in the primary analysis. In addition to the primary analysis, we will also conduct a randomized or classical ITT analysis, which will consider all patients randomized. This will be used as a conservative alternative to our primary comparison. Additionally, we will also perform 2 modified intent-to-treat (mITT) analyses: 1) excluding patients who were withdrawn from the study for any reason (including initial positive CMV LFA test followed with confirmatory negative CMV ELISA test) after receiving at least one dose of study drug, and 2) only including patients who survived and were followed to day 28. We will also test for an interaction of treatment period (pre and post drug use) and the primary treatment differences at the study conclusion. Finally, we will perform subgroup analyses evaluating treatment effect stratified on mode of respiratory support.

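### Subgroup effects are to be examined by separate within-subgroup analyses, and neither supplied document names a treatment-by-baseline-subgroup interaction test

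*Combined protocol and SAP*

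**What the plan says.** Protocol Section 6.2.2 describes the analyses of the secondary endpoints and the covariate-adjusted models, and then says: "We will repeat the above analyses in several subgroups (separately) as well". The first list has seven entries. One is a negative CMV PCR at entry; the protocol words the other six this way: "as well as those that have septic shock, pneumonia, unilateral infiltrates, or lymphopenia at the time of randomization, and by age and sex". A second list follows: "In addition, we will repeat the above analyses in the following subgroups as follows". It has six numbered items, five built on ventilation mode at randomization (some with different endpoints) and one on COVID-19 status. Protocol Section 6.2.4 adds a subgroup analysis stratified on mode of respiratory support.

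In the SAP, Section 9 states for mortality that "subgroup analyses will be conducted stratified by baseline creatinine clearance", with a cut at 60 mL/min. Section 11 says: "Subgroup analyses will be conducted to explore potential treatment effects on RSFDs and mortality". Its factor list differs from the protocol's. It includes site, race, severity scores and underlying conditions, and does not name septic shock, pneumonia or infiltrates. Section 11 places these analyses outside the final study report and leaves their detail to a companion SAP.

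On multiplicity, protocol Section 6.2.2 says: "The multiple testing problem will be handled using a Bonferroni correction, whenever such situations arise". SAP Section 5 says: "Where applicable, Bonferroni correction will be used to adjust for multiple comparisons across secondary endpoints".

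On interaction, protocol Section 6.2.4 says: "We will also test for an interaction of treatment period (pre and post drug use) and the primary treatment differences". SAP Sections 5, 9 and 10 plan a treatment-by-period interaction for mortality. Neither document names an interaction between treatment and a baseline factor.

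**The concern.** A subgroup analysis usually asks whether the treatment effect differs between kinds of patient. A p-value within one stratum answers a different question: whether there is an effect in that stratum. Strata differ in size, so the same true effect can easily be significant in one and not in the other. Several protocol entries also name only one side of a factor (septic shock, pneumonia, unilateral infiltrates, lymphopenia), so the comparison stratum is not specified.

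According to SAP Section 4, enrollment closed on safety and futility concerns. Who was helped or harmed is then a natural question, and SAP Section 11 takes it up for RSFDs and mortality. Without an interaction test, or any rule for reading within-subgroup results, the report would have no valid basis for saying that an effect differs.

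**Working it through.** **1. Inputs.** Difference 2.74 days, SD 9.4 days, two-sided 5% (SAP Section 2.5; protocol Section 6.1.1). Planned allocation 250 per arm (protocol schema). The documents give no observed subgroup sizes, so splits from 50/50 to 12/88 are assumed. The 12/88 end coincides with the roughly 12% expected to be PCR positive at baseline in protocol Section 6.1.1.

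**2. The plan's own figure.** Two-sample noncentral-t power gives 213 per arm for 85% power (computed 0.851). All nine cells of protocol Table 6-2 reproduce exactly. With 250 per arm, power is 0.902.

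**3. Count.** 7 + 6 = 13 entries. The factors are PCR status, septic shock, pneumonia, infiltrates, lymphopenia, age, sex, ventilation mode and COVID-19: 9 factors, with overlapping patients.

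**4. Discordant significance when the effect is the same in both strata.** For a stratum with m patients per arm, the noncentrality is 2.74 / (9.4 × √(2/m)) with 2m − 2 degrees of freedom. The two strata of a factor contain different patients, so

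P(one significant, one not) = p₁(1 − p₂) + p₂(1 − p₁).

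| Split | m per arm | p₁ | p₂ | Discordant |
|---|---|---|---|---|
| 50/50 | 125, 125 | 0.631 | 0.631 | 47% |
| 30/70 | 75, 175 | 0.426 | 0.776 | 54% |
| 20/80 | 50, 200 | 0.303 | 0.828 | 63% |
| 12/88 | 30, 220 | 0.199 | 0.862 | 72% |

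Example, 12/88: 0.199 × 0.138 + 0.862 × 0.801 = 0.718. With 213 per arm the range is 49% to 70%. With no effect in either stratum, discordance is 2 × 0.05 × 0.95 = 9.5%.

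**5. Would Bonferroni cure this?** Take the 13 entries as the family, so each test is at 0.05/13 = 0.00385. For a 50/50 split the power in each stratum falls to 0.272, and discordance is 2 × 0.272 × 0.728 = 40%. The correction lowers power in both strata, and results that disagree by chance remain common.

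**6. The interaction test.** With a uniform effect its false-positive rate is 5% per factor, whatever the split. With SE = 9.4 × √(2/m₁ + 2/m₂) and power ≈ Φ(2.74/SE − 1.96), at 250 per arm:

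| Split | SE (days) | Power for a 2.74-day difference in effect | Difference detectable with 80% power (days) |
|---|---|---|---|
| 50/50 | 1.68 | 37% | 4.7 |
| 30/70 | 1.83 | 32% | 5.1 |
| 20/80 | 2.10 | 26% | 5.9 |
| 12/88 | 2.59 | 18% | 7.2 |

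With 213 per arm, power runs from 32% (50/50) to 16% (12/88).

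**The case against.** The other side has several fair points.

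- **No misreading is planned.** A reader might infer that a chance significant subgroup will be reported as effect modification. Neither document says so or gives any decision rule for subgroup claims, and the SAP calls the Section 11 analyses exploratory. What the documents support is that no valid basis for such a claim is specified.
- **A multiplicity rule exists.** A reader might compute 1 − 0.95^13 = 49% as the chance of at least one false positive. That figure does not measure this problem. It assumes 13 independent, unadjusted tests, whereas the entries are 9 overlapping factors and the section carries a general Bonferroni rule. Thirteen unadjusted interaction tests would give the same 49% under the same assumptions, and nine would give 37%. The rule is nonetheless too vague to apply: no family or number of tests is stated, the SAP words it for secondary endpoints, and step 5 shows that it answers a different question.
- **An interaction test may exist elsewhere.** The companion SAP was not available and could contain one for the Section 11 factors. The creatinine-clearance analysis, however, is in SAP Section 9 with no such deferral, and the protocol's main lists are in its secondary-endpoint section.
- **Not every entry asks about a difference.** Intubation after enrollment exists only for patients on NIV or HFNC. VFDs in ventilated patients and the PCR-negative analysis can be read as estimates in a population of interest. This stands, and it limits the fix.

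**Conclusion.** The point holds as a gap in method. The supplied documents repeat or stratify analyses by baseline subgroup and name no treatment-by-subgroup interaction, although they do name one for treatment period. If the effect were a uniform 2.74 days, separate 5% tests would disagree between two strata about 47% to 72% of the time, against 5% false signals per factor from an interaction test.

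These figures rest on assumed splits, an SD of 9.4 in every stratum, and the planned 250 per arm. They also assume that the planned effect exists; with no effect, disagreement falls to 9.5% per two-level factor. The conclusion covers only the documents supplied. It concerns secondary and exploratory analyses and leaves the primary comparison untouched. The change should still be made, because it is cheap and the present method cannot answer the question.

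**What to change.** For each baseline factor with two or more comparable strata, fit one model with treatment, factor and their interaction: linear for RSFDs, Cox for mortality. This covers creatinine clearance, respiratory-support mode, COVID-19 status, septic shock, pneumonia, infiltrates, lymphopenia, age and sex. Name every level, including the complements that the protocol leaves out. Report the treatment estimate with 95% CI for each level and the interaction p-value. Base any statement of differential effect on the interaction only, label it exploratory, and state that within-subgroup p-values are not evidence that effects differ.

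Keep analyses defined in a single group, such as intubation after enrollment among NIV/HFNC patients, as within-group estimates. Reconcile the protocol and SAP factor lists into one, say whether Bonferroni applies to the subgroup analyses and over which family, and align the companion SAP.

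The cost is a few lines of code and no new data. The drawback is low interaction power (about 18% to 37% for a 2.74-day difference in effect), so fewer subgroup claims can be made, and a non-significant interaction must not be read as proof of a uniform effect.

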4.3.3 Rationale for duration of drug

We chose a study drug duration of until death, hospital discharge, or 28 days (whichever occurs earlier), for several reasons:

- Incident CMV reactivation occurs in critically ill patients up to 28 days after admission [8, 15, 23]; therefore, discontinuing ganciclovir at ICU discharge would leave CMV seropositive patients at risk of CMV reactivation;
- Time-dependent analyses have shown a delay between CMV reactivation and subsequent poor clinical outcomes; thus, early discontinuation of ganciclovir could have a substantial impact on subsequent patient outcomes;
- In our phase 2 study, ~8% of days on invasive mechanical ventilation occurred after initial ICU discharge; this figure is likely similar for days on respiratory support.

Administering ganciclovir was highly feasible across sites in our phase 2 study; 92% of patients received all post-ICU discharge doses, and 84% of post-ICU doses were administered successfully.

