5.3.1 Exploratory Endpoints

1. Static respiratory system compliance at randomization, day 4 and day 7.
2. Invasive bacterial and fungal infections.
3. Organ dysfunction scores (regular SOFA variables including respiratory, coagulation, liver, cardiovascular, CNS and renal; as well as SpO₂/FiO₂ ratio).
4. The NHLBI-endorsed Acute Respiratory Failure Core Outcome Measurement Set (COMS) in survivors at day 180.
5. Risk factors for CMV reactivation (>0 IU/mL, >1000 IU/mL) in plasma and lung
 - a. Sex, age, race
 - b. Co-morbidity
 - c. APACHE III score at baseline
 - d. SOFA score and individual components
 - e. Lymphocyte count
 - f. Time from hospital admission
 - g. Viral load prior to randomization
6. Relationship of CMV viral load with RSFDs and VFDs and secondary clinical outcomes:
 - a. Viral load: initial, peak, slope, area under the curve (AUC)
 - b. Association with RSFD and VFD, day-28 mortality, duration of mechanical ventilation in survivors, static compliance, and PaO₂/FiO₂.
 - c. Baseline viral load in plasma and lung.

7. Viral load kinetics among survivors in day 7 and 14.
8. Sensitivity, specificity, PPV and NPV of rapid lateral flow CMV serostatus assay.
9. CMV cellular immunity, neutralizing antibodies, antibody epitope expansion, and transcriptional signatures.
10. Use of ECMO at any time during the post-randomization period, and duration if used
11. Occurrence of neuromuscular blockade.
12. Prone positioning status.

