We will also compare the duration of mechanical ventilation and respiratory support by day 28 among survivors between the two intervention arms. If the rate of death by day 28 differs between the two groups, then the analysis in survivors may be biased. If there is evidence for a differential death rate, then a sensitivity analysis will be conducted to evaluate how the estimated mean difference changes with a range of assumptions about the degree of possible selection bias. The sensitivity analysis method of Shepherd will be used [91], which was designed to address “truncation by death”. A mediation analysis will also be conducted to test if CMV viremia lies in the causal pathway linking the treatment (Ganciclovir) effect with the outcome (RSFDs), that is,

if CMV viremia, which is assumed to be affected by the treatment, itself affects the outcome or not.

This analysis will be conducted in four steps:

1. A regression analysis with Treatment predicting RSFDs to test for path c alone,
2. A regression analysis with Treatment predicting CMV Viremia to test for path a,
3. A regression analysis with CMV Viremia predicting RSFDs to test the significance of path b,
4. A multiple regression analysis with Treatment and CMV Viremia predicting RSFDs.

The purpose of Steps 1-3 is to establish that zero-order relationships among the variables exist. If one or more of these relationships are non-significant, it can be concluded that mediation is not likely. If there are significant relationships in Steps 1 through 3, Step 4 is conducted. In the Step 4 model, some form of mediation is supported if the effect of CMV Viremia (path b) remains significant after controlling for Treatment. If Treatment is no longer significant when CMV Viremia is controlled, the finding supports full mediation. If effect of CMV Viremia is still significant, the finding supports partial mediation. Apart from this, static respiratory system compliance (Crs) will also be used in a separate mediation analysis to understand whether any effect of Ganciclovir is exerted via pulmonary mechanisms.

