6.2.3 Exploratory endpoints

To identify risk factors for CMV reactivation, we will first build univariate generalized linear regression models to test the association between CMV reactivation and different potential risk factors identified in Section 1 C.2. We will also build multivariate Generalized Linear Models for association with CMV reactivation, by including (i) factors found significant at level 0.2 in the first step and (ii) all risk factors, and then using a step-wise backward selection using the Akaike Information Criterion (AIC) or the Bayesian Information Criterion (BIC) for model selection.

We will use descriptive statistics and plots to examine the association of CMV viral load kinetics in blood and lung compartments with RSFDs and VFDs, mortality at day 28 and 180, duration of respiratory support in survivors, PaO₂/FiO₂, and static respiratory system compliance. We will also build regression models (generalized linear models) to examine these relationships more closely. We will also descriptively determine the sensitivity and specificity of the rapid lateral flow CMV serostatus assay, and assess its concordance with the standard clinical assays, using Cohen's kappa statistic.

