10.1 Laboratory procedures

Laboratory procedures include but are not limited to:

- Baseline whole blood sample for immunity and biomarker studies.
- ETA at baseline (\pm 1 day of randomization) and then twice weekly (\pm 2 days) while the patient is intubated for CMV viral load, inflammatory biomarkers, characterization of cellular content.
- Aliquot of BALF and/or lung biopsy done for clinical purposes. For patients who undergo lung biopsy or autopsy, a sample of lung tissue (frozen or fresh) is requested.
- Blood samples at baseline, then:
 - Weekly (twice weekly in intensified monitoring subset) until day 28 or hospital discharge, whichever happens first.
 - For CMV viral load, cytokine analysis, and safety labs (CBC with neutrophil count and platelets, and creatinine).
 - Samples for studies to assess CMV-specific immunity and transcriptomics will be collected at selected sites that have the capability for sample processing
- Bacteremia/fungemia and nosocomial pneumonia (including ventilator-associated pneumonia) will be assessed by clinical testing.

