APPENDIX A: TIME AND EVENTS SCHEDULE

Visit	Screening	01	02	03	04	05	06	07	08	09	10	Assay Location
Day	-4 to 1	1	4	7	11	14	18	21	25	28	180	
Window (+/- days)	0	1	1	1	1	1	1	1	1	4	42	
Informed consent	X	-	-	-	-	-	-	-	-	-	-	
Administer Study Drug		Patient receives 5 days of ganciclovir (or placebo) intravenously TWICE daily, then up to 23 additional days of ganciclovir (or placebo) intravenously ONCE daily in hospitalized patients.										
Blood collection (ml) vol. estimated:												
Pregnancy testing	3 ^a			3 ^b								L
CMV Serology	3	-	-	-	-	-	-	-	-	-	-	L/A
Genomic analysis sample ^c	-	5	-	-	-	-	-	-	-	-	-	S
T cell immunity samples ^{c,e,m}	-	(30)	-	-	-	-	-	-	-	-	-	S
Serum Creatinine ^{d,n}	1	1	1	1	1	1	1	1	1	1	-	L
CMV PCR (plasma) ^{d,c}	-	5	(5)	5	(5)	5	(5)	5	(5)	5	-	S
CBC, w/diff, platelets ^d	1	3	3	3	3	3	3	3	3	3	-	L
Blood volume (estimate)	8	14 (44)	4 (9)	9	4 (9)	9	4 (9)	9	4 (9)	9	-	
Endotracheal aspirate (ETA)												
CMV PCR ^{e, f}	-	X	(X)	(X)	(X)	(X)	(X)	(X)	(X)	(X)	-	S
Clinical Assessments:												
SOFA ^g and, fluid balance		Daily on Days 1-7			X	X	X	X	X	X		
Ventilator (including static compliance), ^f NIV, HFNC parameters, and FiO ₂		Daily										
Antiviral, antibacterial or antifungal medications ^h		Daily on Days 1-7			X	X	X	X	X	X		
Apache III		X										
AE/SAE monitoring		X	X	X	X	X	X	X	X	X		
ECMO, prone positioning, steroids, immunosuppressive medications, and neuromuscular blockers		X	At any time while on study; collected at discharge									
Vital status			ICU and hospital mortality collected at discharge									X
Bacteremia, fungemia, nosocomial pneumonia (including ventilator-associated pneumonia)			At any time while on study; collected at discharge									
Contact (e.g. phone)										X ⁱ	X ^k	
NHLBI COMS survey		X ^l									X ^l	

L = local test; S=Seattle, WA; A= ARUP in Utah

^a Pregnancy tests (serum or urine) performed within 120 hours before enrollment are acceptable.

^b At day 7 or discharge, whichever is earlier (if day 7 is missed, at discharge is acceptable). Only serum test is acceptable.

- c All samples will be stored for analysis at the end of the study
- d All blood draws will occur only during hospitalization, blood chemistry, CBC and platelet values can be obtained from clinical testing result if available, thereby reducing required blood volume
- e Time points in () only in patients with intensified monitoring (n=150).
- f Can only be collected if subject is ventilated
- g While in the ICU

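### CMV sampling stops at discharge, so regressing RSFDs on viremia or whole-period viral load can be significant when CMV has no effect

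*Combined protocol and SAP*

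**What the plan says.** Protocol Section 6.2.2 sets out a four-step mediation analysis. Step 3 is "A regression analysis with CMV Viremia predicting RSFDs to test the significance of path b". Step 4 puts treatment and viremia in one model, and "some form of mediation is supported if the effect of CMV Viremia (path b) remains significant after controlling for Treatment". Step 4 is reached only if Steps 1 to 3 are all significant: "If one or more of these relationships are non-significant, it can be concluded that mediation is not likely". The viremia variable has no stated metric or time window.

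Separately, exploratory endpoint 6 (Section 5.3.1) relates RSFDs and other outcomes to "Viral load: initial, peak, slope, area under the curve (AUC". Section 6.2.3 begins with descriptive statistics and plots, then adds: "We will also build regression models (generalized linear models) to examine these relationships more closely".

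On sampling, Appendix A note d says "All blood draws will occur only during hospitalization". Section 10.1 runs the weekly draws (twice weekly in the intensified subset) "until day 28 or hospital discharge, whichever happens first". Endotracheal aspirates are taken only while the patient is intubated. Sections 9.9 and 9.11 are looser: one ties PCR samples to being on study, and the other expects missed draws after discharge.

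Protocol Section 6.4.1.2 and SAP Section 3.2 recognise that discharge, extubation or death removes specimens. They offer imputation without choosing a method, or a stated limitation; the SAP adds sensitivity analyses. The SAP does not carry the mediation analysis forward, but its section on changes from the protocol does not withdraw it.

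**The concern.** RSFDs count back from day 28 to the last day of support. Patients who recover quickly go home and stop being sampled, while patients who recover slowly keep being sampled. The number of chances to detect viremia is therefore partly set by the outcome it is meant to predict. Slow recovery does not create more viremia, but it does lead to more viremia being detected, and to higher observed peaks and larger AUCs.

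The protocol knows that timing matters. In Section 4.3.3 it argues for 28 days of drug because "Time-dependent analyses have shown a delay between CMV reactivation and subsequent poor clinical outcomes". Yet Steps 3 and 4 and the viral-load models contain no landmark, time-dependent term or adjustment for time under observation. At stake is the trial's account of mechanism: a sampling artefact could be read as evidence that CMV reactivation worsens respiratory outcome.

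**Working it through.** The documents give no figure for the mediation analysis. For scale, the trial is powered for 2.74 RSFDs with SD 9.4. A noncentral-t calculation at 85% power and two-sided 5% returns the plan's 213 per arm.

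**Inputs from the documents.** Day-28 mortality about 20% (Section 6.1.2). Deaths score zero RSFDs (5.1.2). Baseline PCR positivity 12% (6.1.1). Overall reactivation about 40%, viremia at least 30% (2.4.1). Plasma at baseline and days 7, 14, 21 and 28 while in hospital (9.11, Appendix A).

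**Step 1: sampling opportunity.**
- Off support after day 4, home by day 6: RSFD = 28 − 4 = 24, with no post-baseline draw.
- Supported on days 1 to 25: RSFD = 28 − 25 = 3, with draws on days 7, 14 and 21, and on day 28 if still in hospital.
- Dead on day 6: RSFD = 0, with the baseline draw only.

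**Step 2: chance of being counted viremic if CMV is inert.** Assume a constant hazard h that takes 12% at baseline to 40% by day 28:

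0.88 × exp(−28h) = 0.60, so h = ln(0.88/0.60)/28 = 0.383/28 = 0.0137 per day.

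The chance of onset by the last draw on day t is P(t) = 0.12 + 0.88 × (1 − exp(−ht)). Ignoring episodes that clear between draws:

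| Last draw | Baseline | Day 7 | Day 14 | Day 21 | Day 28 |
|---|---|---|---|---|---|
| P(t) | 12% | 20% | 27% | 34% | 40% |

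The fast recoverer has a 12% chance and the slow one 34% to 40%, with no effect of CMV. The early death also has 12%, but with zero RSFDs, so it pulls the other way.

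**Step 3: false rejection of path b.** I simulated 250 per arm with the CMV course independent of recovery and death. Assumptions not in the documents: survivors' support lognormal, median about 6 days; discharge on average 5 days after support ends; mean day of death about 11; ganciclovir cuts the reactivation hazard by 75%; episodes last about 10 days on ganciclovir and 17 on placebo. Simulated placebo RSFDs had mean 15.3 and SD 9.8, against 16.33 and 9.62 for VFDs in Table 6-1. Step 4 results for any viremia at nominal 5%:

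| Setting | Full population: rejection (coefficient) | Day-28 survivors: rejection |
|---|---|---|
| Base case | 13% (−1.0 day) | 51% |
| Discharge lag 2 days | 26% (−1.5) | 62% |
| Discharge lag 10 days | 6–7% (−0.3) | 36–37% |
| Mean death day about 7 | 6% (−0.5) | 50% |
| Mean death day about 16 | 25–26% (−1.5) | 54% |
| 30% reactivation | 10% (−0.8) | 30% |
| 35% mortality, early deaths, lag 10 | 13% (+1.1) | 30% |

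In the base case, peak gave 14% and AUC 46% in the full population, and 57% and 97% in survivors. Twice-weekly draws did not help (13% for any viremia).

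A second design used 250 participants, 12% baseline positivity, survivors' support matched to Table 2-1 (median 6.5, IQR 3–12.25), mortality 15–30%, discharge 3 or 7 days after support, and deaths spread evenly over days 2–28. It gave roughly 15% to 80%. Even spacing makes deaths late, which weakens their opposing pull: with 20% mortality and a 7-day lag, moving the mean death day to about 11, 8 and 6 gave 11–15%, 8–10% and 5–6%. A third run at 20% mortality gave 9–73% in the full population and 73–92% in survivors.

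**Step 4: the whole four-step verdict.** If ganciclovir has no effect on RSFDs, Step 1 holds the false-positive rate to at most 5%. If it moves RSFDs by about 2.8 days by a non-CMV route, all four steps are positive in 8% (any viremia), 8% (peak) and 38% (AUC) of trials in the full population, and in 41%, 40% and 95% among survivors. For any viremia in the full population this is 12% at a 2-day lag and under 4% at a 10-day lag.

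**Step 5: candidate repairs.**
- Day-7 landmark: 4–6% in every setting above and 3–6% in the third run, coefficient about 0.
- Last observation carried forward: any viremia and peak cannot change. AUC falls to about 5% (2–3% in survivors).
- Sampling everyone to day 28 regardless of discharge: 6% in survivors, but 52% in the full population with the sign reversed (+2.0 days), because deaths still have short sampling and zero RSFDs.

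**The case against.** A reader might infer that a null trial could be explained away by a spurious CMV pathway. The mediation steps do not support that: without a significant treatment effect at Step 1, the plan ends at mediation being unlikely. That stands, and it limits the mediation part of the point. The exploratory regressions have no such precondition.

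A reader might also take peak and AUC to be the mediator. They belong to exploratory endpoint 6, and the mediation paragraph names no metric. The day-28 window is inferred from the sampling schedule. Nor can one assume a bias towards fewer RSFDs in every population. With early deaths it nearly vanishes or changes sign, so no single rejection rate can be quoted.

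The plan is not silent on missing specimens, and carrying observations forward would largely repair AUC. Baseline viral load, also listed, is free of the problem. The SAP refers additional analyses to a companion exploratory document that is not available here, so the metric may be defined there. All this narrows the point. It does not supply a rule for unequal sampling time in the analyses as written.

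**Conclusion.** The point holds as a fault in secondary and exploratory analyses. Detection of viremia depends on length of stay, length of stay depends on RSFDs, and Steps 3–4 and the post-baseline viral-load models ignore this. With no CMV effect and 12% positive at baseline, the any-viremia test rejects in about 6% to 80% of trials in the full population. Among day-28 survivors it rejects in about 36% to 92%, falling to about 30% with low reactivation or with heavy early mortality and long stays; the direction there is consistently negative. A coefficient whose size and sign turn on discharge lag and death timing cannot be read as a CMV effect. The ranges rest on assumed stays, death times and viral courses. It would be wrong to infer that the primary comparison or the sample size is compromised: neither uses viremia.

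**What to change.** For mediation Steps 3–4 and exploratory endpoint 6, define the viremia metric and window, and replace whole-period viremia, peak, slope and AUC as predictors by one of:

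- (a) A day-7 landmark: participants alive and in hospital at day 7, with viremia or viral load at baseline and day 7 predicting later outcome, and a treatment term. Day-7 plasma is scheduled at all sites.
- (b) Viremia as a time-dependent covariate for time to final liberation from support, with death as a competing event and the end of sampling at discharge handled explicitly.

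Keep baseline viral load as a predictor. Show whole-period peak, slope and AUC descriptively only. Reconcile Sections 9.9 and 9.11 with Appendix A note d on when draws stop.

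The cost is wording and modest analysis time, with no new data. The analysis is smaller: about 70% to 85% of simulated participants reached the landmark at discharge lags of 2 to 10 days. Option (a) misses reactivation after day 7 and leans on baseline positives, since Section 4.4 expects fewer than 8% to reactivate in plasma before day 5. The landmark set is selected after randomisation, so its treatment coefficient is not a randomised comparison and should be labelled so.
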